## 10.2 Synovial Sarcoma (Treatment Group 2)

Treatment Cycle	Screening	Base line/ IFN lead-in	1	2	3	4	5	6	7	8	9	10	Subsequent Cycles (up to 2 years)	End of Tx and at documented progression	Post Treatment Follow-up		
Weeks			1-3	4-6	7-9	10-12	13-15	16-18	19-21	22-24	25-27	28-30		At the time of D/C	Safety FU	Disease Assessment a	Survival FU
Scheduling window (days)	Within 7 days		+/- 3d	+/- 7d			30 d +/- 5d post D/C	Every 12 +/- 1 weeks	Every 12 +/- 1 weeks								
Interferon-gamma (ACTIMMUNE) b		X	X	X	X	X	X	X	X	X	X	X					
MK-3475 (pembrolizumab) c			X	X	X	X	X	X	X	X	X	X					
Administrative procedures																	
Informed consent	X																
Demographics	X																
Medical history	X																
Concurrent meds	X	X	X	X	X	X	X	X	X	X	X	X	X	X	X	X	X
Clinical Procedures/Assessment																	
Physical exam	X	X	X	X	X	X	X	X	X	X	X	X	X	X	X		
Vital signs and weight	X	X	X	X	X	X	X	X	X	X	X	X	X	X	X	X	
Height	X																
ECOG Performance status	X	X	X	X	X	X	X	X	X	X	X	X	X	X	X	X	
EKG d	X																
Adverse event assessment			X	X	X	X	X	X	X	X	X	X	X	X	X	X	
Pulmonary function testing e	X																
Laboratory Assessments (Safety Labs)																	
CBC w/diff	X	X	X	X	X	X	X	X	X	X	X	X	X	X	X	X	
Serum chemistry f	X	X	X	X	X	X	X	X	X	X	X	X	X	X	X	X	
Pregnancy test (urine or serum HCG) g	X																
Urinalysis	X							X					X h				
T3, FT4 and TSH	X							X					X h				

NCI Protocol #: CITN-13  
 Version Date: March 03, 2020

Treatment Cycle	Screening	Base line/ IFN lead-in	1	2	3	4	5	6	7	8	9	10	Subsequent Cycles (up to 2 years)	End of Tx and at documented progression	Post Treatment Follow-up		
Weeks			1-3	4-6	7-9	10-12	13-15	16-18	19-21	22-24	25-27	28-30		At the time of D/C	Safety FU	Disease Assessment a	Survival FU
Scheduling window (days)	Within 7 days		+/-3d	+/- 7d	+/- 7d	+/- 7d	+/- 7d	+/- 7d	+/- 7d	+/- 7d	+/- 7d	+/- 7d			30 d +/- 5d post D/C	Every 12 +/- 1 weeks	Every 12 +/- 1 weeks
Efficacy Measurements																	
Radiologic evaluation	X i					X				X		X j	X		X		
Tumor Biopsies/Archival Tissue Collection																	
Tumor biopsy	X k				X l												
Correlative Studies Blood Draws																	
Tetramer analyses by Flow Cytometry m		X n			X				X				X				
Whole Blood Multiparametric Flow cytometry m		X n	X		X				X								
ELISPOT m		X n			X				X				X				
Multiplex cytokines m		X n	X		X				X				X				
HLA Typing o		X n															
Stool Sample																	
Microbiome p		X															

- a. Disease assessment per standard of care
- b. Interferon Gamma-1b: 100 mcg/m^2 once per week, starting one week prior to the first MK-3475 (pembrolizumab) dose.
- c. MK-3475 (pembrolizumab): 200 mg ( $\geq 18$  years of age)/2 mg/kg (max=200mg) ( $< 18$  years of age) every 3 weeks, starting cycle 1, week 1, day 1.
- d. Electrocardiogram will be performed at screening. Repeat only if clinically indicated.
- e. Pulmonary function testing required at baseline only for patients with a history of significant pulmonary disease, prolonged smoking history, or symptoms of respiratory dysfunction.
- f. Albumin, alkaline phosphatase, total bilirubin, bicarbonate, BUN, calcium, chloride, creatinine, glucose, LDH, phosphorus, potassium, total protein, SGOT [AST], SGPT [ALT], sodium.
- g. Pregnancy test (women of childbearing potential) must be performed within 72 hours of the initiation of study treatment.
- h. Urinalysis and thyroid (T3, FT4 and TSH) function tests will be performed every 6th cycle.
- i. Baseline radiographic assessment by CT scan must be done  $< 2$  weeks (14 days) before the initiation of study treatment.
- j. Radiographic assessment by CT scan will occur every 12 weeks (+/- 1 week).
- k. Baseline tumor biopsy (archival or fresh) is mandatory. Although there is no time limit on the pretreatment biopsy, the patient cannot have undergone a different therapy since its collection. Archival tissue can be used in lieu of a pretreatment biopsy if the patient has not undergone any treatment since that tissue was collected. If a fresh baseline biopsy is

NCI Protocol #: CITN-13  
 Version Date: March 03, 2020

Treatment Cycle	Screening	Base line/ IFN lead-in	1	2	3	4	5	6	7	8	9	10	Subsequent Cycles (up to 2 years)	End of Tx and at documented progression	Post Treatment Follow-up		
Weeks			1-3	4-6	7-9	10-12	13-15	16-18	19-21	22-24	25-27	28-30		At the time of D/C	Safety FU	Disease Assessment a	Survival FU
Scheduling window (days)	Within 7 days		+/-3d	+/- 7d			30 d +/- 5d post D/C	Every 12 +/- 1 weeks	Every 12 +/- 1 weeks								

obtained this should be collected any time after confirmation of eligibility and before the first dose of interferon gamma-1b.

1. The second biopsy is mandatory for participant  $\geq 18$  years of age, but will be performed only if deemed safe by the principal investigator. For participants  $< 18$  years of age a second biopsy is optional, and will be performed only if deemed safe by the principal investigator. The second biopsy will be performed after week 8, but before the patient's first scan at week 12.
- m. Correlative blood samples must be drawn prior to administration of study agents on a dosing day.
- n. Baseline correlative samples to be collected prior to the first dose of Interferon Gamma-1b.
- o. HLA-typing is performed on residual material from the flow cytometry blood draws. There is no additional blood draw for this test.
- p. Fecal swab/storage instructions must be given to patient; sample collection to be performed at home by patient and returned to clinical research site at the next study visit.

## 11. MEASUREMENT OF EFFECT

### 11.1 Mycosis Fungoides/Sézary Syndrome (Treatment Group 1)

#### 11.1.1 Antitumor Effect – Solid Tumors

Mycosis Fungoides and Sézary Syndrome are unique in that some patients will not have disease that is measurable by CT or PET/CT. Patients who have cutaneous disease only will not have measurable disease by CT or PET/CT. Patients with measurable disease will have scans at the intervals specified in the study calendar. Patients who have nonmeasurable disease by CT and/or PET CT will have a scan at baseline (before study drug is initiated). This scan will be done as standard of care before study entry and will be used to determine the presence or absence of measurable disease. Subsequent scans in patients with nonmeasurable disease will only occur at CR, PR, PD/EOT.

There will be other criteria in addition to standard radiographic evaluation used in this study to determine progression or regression of disease including mSWAT (modified severity-weighted assessment tool) to determine response in skin. Flow cytometry will be used to determine the number of circulating Sézary cells (CSC's) in the blood in order to evaluate response. Lastly, all of the measures including Skin (mSWAT), Lymph Nodes (CT or PET/CT), Visceral Disease (CT or PET/CT) and Blood (Flow Cytometry) will be combined to determine a Global Response Score. All of these evaluations, including the Global Response Score will be described in further detail in this section of the protocol.

Patients will be assessed (including scans for measurable disease, mSWAT and CSC, for extracutaneous disease) before study drug at Cycle 6, 10, then every 4 cycles thereafter. If progression is noted at an assessment, a confirmatory assessment will be repeated in  $\geq 4$  weeks. Assessments will also be performed at the time of CR/PR confirmation, PD and at EOT. Note: Only patients with extracutaneous disease (measurable by CT scan) will have scans done at these specified intervals. Those with nonmeasurable disease are only scanned at baseline, then at CR, PR, PD/EOT.

If a CR is achieved patients may stop study drug therapy after 2 additional cycles (each cycle is 3 weeks) have been given after 6 months of therapy have been completed. (i.e., 6 months + 2 cycles). If patients who have stopped after a CR have disease recurrence, they may re-start therapy if they have not received additional therapy in the interim, if they are still eligible for the trial and the trial is still open to enrollment.

##### 11.1.1.1 *Definitions*

Evaluable for toxicity. All patients will be evaluable for toxicity from the time of their first treatment with Interferon-gamma (given first as run-in before MK-3475 (pembrolizumab)).

Evaluable for objective response. As described above patients enrolled in this trial may not have disease that is measurable by CT and/or PET/CT however they can still

be objectively evaluated for disease response using parameters unique to Mycosis Fungoides/Sézary Syndrome.

11.1.1.2 *Disease Parameters: N/A*

11.1.1.3 *Tumor Imaging and Assessment of Disease*

The primary outcome is antitumor effect. Definitions for global response, CR, PR, PD, and SD (in skin/LN/viscera/blood) are detailed here.

*Measurement Methods*

- Skin: mSWAT.
- Lymph nodes: CT or PET/CT (Olsen criteria).
- Viscera: CT or PET/CT (Olsen criteria).
  - If using a PET/CT the CT should be of diagnostic quality
- Blood: Flow cytometry.

The skin compartment is the target of primary efficacy assessment, however in those subjects with extracutaneous disease, all involved compartments will be assessed separately and a global response will be determined.

Clinical response in the skin compartment will be assessed according to changes in the modified Severity-Weighted Assessment Tool (mSWAT) [Appendix E] and documented as SD, PR, complete clinical response, or PD as defined below. The response in the lymph node compartment will be assessed by IWG criteria, in blood by flow cytometry, and global response will be assigned adhering to the consensus criteria below. All objective response (PR or CR) and progression (PD) must be confirmed after 4 weeks. Digital copies of mSWAT photographs will be retained at sites for quality assurance or secondary review purposes.

Regardless of treatment delays, response assessment including mSWAT, circulating sézary cell count and imaging should always be performed on the aforementioned schedules. (i.e., the imaging and mSWAT schedules do not change if there are treatment delays). Subjects with CR after receiving a minimum of 6 months of treatment with at least 2 doses since CR may discontinue therapy. Subjects with a CR who progress may be retreated if (1) no cancer treatment was administered since the last dose of MK-3475 (pembrolizumab), (2) subject continues to meet eligibility criteria, and (3) the trial is open. Subjects without symptomatic progression may receive up to a maximum of 2 years if radiologically and clinically improving or stable after 12 cycles.

11.1.1.4 *Initial Tumor Imaging*

Initial tumor imaging with a CT or PET/CT must be performed within 28 days before the first dose of trial treatment. For subjects with documented extracutaneous disease imaging will be repeated at the intervals specified in [section 11.1](#). For consistency in interpretation, perform the same type of radiologic evaluation that was performed at screening. All subjects on the trial will have an EOT scan. Scans performed as part of routine clinical management are acceptable for use as the screening scan if they are of

diagnostic quality and performed within 28 days before the first dose of trial treatment. Imaging timing should follow calendar days and should not be adjusted for delays in cycle starts or extension of MK-3475 (pembrolizumab) cycle frequencies. The same imaging technique should be used in a subject throughout the trial. The site study team must review pre-trial images to confirm the subject has measurable disease per Olsen criteria **if the patient is going to be entered on trial with radiographically measurable disease**. Patients with only cutaneous disease (nonmeasurable by CT) are also eligible for the study.

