##### **5.3.1.2 *Prohibited Concomitant Medications***

Patients are prohibited from receiving the following therapies during the Screening and Treatment Phase (including retreatment for post-complete response relapse) of this trial:

- Antineoplastic systemic chemotherapy or biological therapy.
- Immunotherapy not specified in this protocol.
- Chemotherapy not specified in this protocol.
- Investigational agents other than MK-3475 (pembrolizumab) and Interferon-gamma (Actimmune).
- Radiation therapy

**Note:** Radiation therapy to a symptomatic solitary lesion or to the brain may be considered on an exceptional case by case basis after consultation with CTEP. The patient must have clear measurable disease outside the radiated field. Administration of palliative radiation therapy will be considered clinical progression for the purposes of determining PFS.

- Live vaccines within 30 days before the first dose of trial treatment and while participating in the trial. Examples of live vaccines include, but are not limited

to, the following: measles, mumps, rubella, chicken pox, yellow fever, rabies, *Bacillus Calmette–Guérin (BCG)*, and typhoid (oral) vaccine. Seasonal influenza vaccines for injection are generally killed virus vaccines and are allowed; however, intranasal influenza vaccines (e.g., *Flu-Mist*®) are live attenuated vaccines, and are not allowed.

- Systemic glucocorticoids for any purpose other than to modulate symptoms from an event of suspected immunologic etiology or for physiologic replacement using 10mg/day or less of Prednisone or equivalent. The use of physiologic doses of corticosteroids may be approved after consultation with the study PI and CTEP.
- **NOTE:** For the synovial sarcoma patients in this trial, systemic glucocorticoids used for  $\leq$  10 days for acute inflammatory symptoms (e.g., allergic reaction), or used at a low dose (prednisone  $\leq$  10 mg/day or equivalent) for physiologic replacement may be administered at the discretion of the treating physician.

Patients who, in the assessment by the investigator, require the use of any of the aforementioned treatments for clinical management should be removed from the trial. Patients may receive other medications that the investigator deems to be medically necessary.

The Exclusion Criteria describes other medications which are prohibited in this trial.

There are no prohibited therapies during the Post-Treatment Follow-up Phase.

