## **5.5 Duration of Follow-Up (Treatment Group 1 and 2)**

All patients, regardless of reason for discontinuation from study, will be followed for AE/SAE resolution for 30 days after removal from study. All patients will be followed for survival either by in-person visit or by telephone assessment every 12 weeks until 1 year after EOT.

Disease status and overall survival data will be collected and reported every 12 weeks, either by in-person visit or by telephone assessment.

After disease progression or start of new anticancer treatment, patient will be followed for overall survival only. Survival follow-up will continue until death or 1 year after the end of treatment, whichever occurs first.

In subjects who discontinue study therapy without documented disease progression, every effort should be made to continue monitoring their disease status by Olsen assessment (for patients with Mycosis Fungoides) or by CT scan (for patients with synovial sarcoma) every 12 weeks ( $\pm$  7 days) until (1) the start of new anticancer treatment, (2) documented disease progression, (3) death, or (4) the end of the study, whichever occurs first. If a previous assessment was obtained within 4 weeks before the date of discontinuation, then an additional assessment at treatment discontinuation isn't mandatory.

Patients removed from study for unacceptable AE(s) will be followed until resolution or stabilization of AE; in addition the patients will be followed for disease status and overall survival, as described above.

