***Continuation after confirmation of progression:***

Patients who are determined to have confirmed progression may continue to receive study treatment if they are clinically stable as defined by the following criteria:

- Absence of signs and symptoms (including worsening of laboratory values) indicating disease progression
- No decline in ECOG performance status
- Absence of rapid progression of disease
- Absence of progressive tumor at critical anatomical sites (*e.g.*, cord compression) requiring urgent alternative medical intervention

The following assessment and stopping criteria apply to patients who continue study treatment beyond progression:

- Patients who continue therapy after progression will have mSWAT performed with every cycle (every 3 weeks) and a full Olsen Criteria assessment including mSWAT, CT scans, for those with measurable disease, and CSC, if positive for Sézary cells, every 4 cycles (every 12 weeks). At the discretion of the investigator these assessments may be repeated more frequently.
- Study drug will be discontinued if any compartment increases in value by 25% or more over the new baseline including mSWAT score, measurable disease by CT scan, or Circulating Sezary Cell Counts. The new baseline being defined as the assessments obtained at the confirmation of progression.

	Clinically Stable		Clinically Unstable	
	Imaging	Treatment	Imaging	Treatment
1st evidence of PD** (Based upon Olsen Criteria including scans (if applicable), mSWAT and Circulating Sézary Cells)	Repeat assessment at approximately 4 weeks to confirm PD	May continue study treatment at the Investigator's discretion while awaiting confirmatory assessment	Repeat assessment at approximately 4 weeks to confirm PD if possible	Discontinue treatment
Repeat assessment confirms PD**	If patient continues with study therapy, repeat mSWAT every cycle. mSWAT, CT scans, for measurable disease, and CSC, for patients who are positive, will be repeated every 4 cycles	Patient may continue therapy with MK-3475.	No additional assessments required	N/A

	(every 12 weeks) Must stop if any compartment increases by 25% or more.			
Repeat assessment shows SD, PR, or CR**	Continue regularly scheduled assessments per the study calendar	Continue study treatment at the Investigator's discretion	Continue regularly scheduled assessments per the study calendar	May restart study treatment if condition has improved and/or clinically stable per Investigator's discretion

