##### *Measurement Methods*

- Lymph nodes: CT or PET-CT (Olsen criteria).
- Viscera: CT or PET-CT (Olsen criteria).

If using a PET/CT the CT should be of diagnostic quality. Imaging should continue to be performed until documented disease progression, the start of new anticancer treatment, withdrawal of consent, death, or the end of the study, whichever occurs first. Disease progression should be confirmed at least 4 weeks after the first scan indicating PD in clinically stable subjects. Subjects who have unconfirmed disease progression may continue on treatment until progression is confirmed.

*Conventional CT and MRI.* This guideline has defined measurability of lesions on CT scan based on the assumption that CT slice thickness is 5 mm or less. If CT scans have slice thickness greater than 5 mm, the minimum size for a measurable lesion should be twice the slice thickness. MRI is also acceptable in certain situations (e.g., for body scans).

*PET-CT.* At present, the low dose or attenuation correction CT portion of a combined PET-CT is not always of optimal diagnostic CT quality for accurate measurement. However, if the site can document that the CT performed as part of a PET-CT is of identical diagnostic quality to a diagnostic CT (with IV and oral contrast), then the CT portion of the PET-CT can be used for tumor measurements and can be used interchangeably with conventional CT in accurately measuring cancer lesions over time. Note, however, that the PET portion of the CT introduces additional data which may bias an investigator if it is not routinely or serially performed.

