**Global Response Score**

Global Score*	Definition	Skin	Nodes	Blood	Viscera
CR	Complete disappearance of all clinical evidence of disease	CR	All categories have CR/NI		

Global Score*	Definition	Skin	Nodes	Blood	Viscera
PR	Regression of measurable disease	CR	All categories do not have a CR/NI and no category has a PD		
		PR	No category has a PD and if any other category involved at baseline, at least one has a CR or PR		
SD	Failure to attain CR, PR or PD representative of all disease	PR	No category has a PD and if any other category involved at baseline, no CR or PR in any		
		SD	CR/NI, PR, SD in any category and no category has a PD		
PD	Progressive disease	PD in any category			
Relapse	Recurrence disease in prior CR	Relapse in any category			

NI= noninvolved

\*It is recommended that not only the proportion of subjects who achieve a response or an unfavorable outcome be calculated but a life table account for the length of the interval.

After the first documentation of progression, it is at the discretion of the investigator to keep a clinically stable subject on trial treatment or to stop trial treatment until repeat imaging performed at least 28 days later confirms progression. A subject with *unconfirmed* progression of disease may continue trial treatment until progression of disease is confirmed. Subjects with suspected pseudoprogression should have biopsy proven confirmation of progression of disease during the 4-week interval between initial demonstration of progression and confirmation of progression of disease. Biopsy findings consistent with pseudoprogression, including evidence of a lymphoid infiltrate, necrotic tumor, without significant increase in viable tumor at site of suspected pseudoprogression, may justify continued treatment at the discretion of the PI.

Subjects may only receive study treatment while waiting for confirmation of PD versus pseudoprogression if the following criteria are met:

- Absence of signs and symptoms indicating disease progression
- Absence of rapid progression of disease
- Absence of progressive tumor at critical anatomical sites (e.g., cord compression) requiring urgent alternative medical intervention

Disease assessments during the follow-up period is to be repeated every 12 weeks ( $\pm 7$  days) for subjects who discontinue trial treatment for reasons other than disease progression until the subject experiences confirmed disease progression or starts a new antineoplastic therapy.

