##### *Progression-free survival (PFS)*

is defined as the time from enrollment to PD or death, whichever occurs earlier, based upon investigator assessment. Patients without documented PD/death will be censored at the last disease assessment date.

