**Summary Analysis Strategy for Efficacy Endpoints**

Endpoint/Variable (Description, Time Point)	Statistical Method	Analysis Population	Missing Data Approach
Primary:			
Overall response rate (ORR) per global assessment of Mycosis Fungoides and Sézary Syndrome (confirmed & investigator assessed)	Binomial proportion	Evaluable population as defined	Subjects without any efficacy evaluation will be excluded; if one compartment is missing data, that compartment will be considered non-response
Secondary:			
Time to Response (TTR)	Simple statistics	All responders	Non-responders are excluded in analysis
Duration of Response (DOR)	Kaplan-Meier method	All responders	Non-responders are excluded in analysis; censored at last f/u or start of new significant therapy
Progression-free survival	Kaplan-Meier method	All efficacy or safety evaluable patients	Censored at last f/u or start of new significant therapy

Endpoint/Variable (Description, Time Point)	Statistical Method	Analysis Population	Missing Data Approach
Event-free survival	Kaplan-Meier method	All efficacy or safety evaluable patients	Event is defined by early termination due to toxicity, start of new significant therapy, PD, or death of any cause
Rate of overall response duration beyond 12 months (ORR12) per global assessment of Mycosis Fungoides and Sézary Syndrome (confirmed & investigator assessed)	Binomial distribution	Evaluable DOR beyond 12 months for evaluable population.	Subjects without any efficacy evaluation will be excluded; The ORR12 is the proportion of ORR times conditional probability of DOR beyond 12 months. If one compartment is missing data, that compartment will be considered non-response. Censored at last f/u. Start of new significant therapy before 12 months will be considered as failures.

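### Group 1 PFS: the plan does not say whether an unconfirmed progression counts, and its literal confirmation rule would censor unstable patients who switch therapy early

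*Combined protocol and SAP*

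**What the plan says.** All references are to Treatment Group 1 in the combined protocol and SAP.

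**Confirmation.** Section 11.1.1.3 sets a rule without exceptions: "All objective response (PR or CR) and progression (PD) must be confirmed after 4 weeks". Section 11.1.1.5 is narrower: "Disease progression should be confirmed at least 4 weeks after the first scan indicating PD in clinically stable subjects".

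**Unstable patients.** The table in Section 5.8.1 has a clinically unstable patient discontinue treatment at first evidence of progression. The assessment cell for that patient reads "Repeat assessment at approximately 4 weeks to confirm PD if possible".

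**After stopping.** Section 5.3.1.2 says: "There are no prohibited therapies during the Post-Treatment Follow-up Phase". Section 5.5 says: "After disease progression or start of new anticancer treatment, patient will be followed for overall survival only". The text after the Global Response Score table in Section 11.1.1.6 continues off-treatment assessments "until the subject experiences confirmed disease progression or starts a new antineoplastic therapy", whereas Section 5.5 ends them at documented progression.

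**PFS analysis.** Section 13.1.1.2 defines PFS by investigator-assessed progression or death and adds: "Patients without documented PD/death will be censored at the last disease assessment date". The Summary Analysis Strategy for Efficacy Endpoints table in Section 13.1.1 gives another rule. Its DOR row reads "censored at last f/u or start of new significant therapy", and its PFS row says the same.

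**Neighbouring rules.** Section 5.3.1.2 counts palliative radiation as progression for PFS. The EFS row counts new significant therapy as an event. The ORR12 row counts it as a failure if it starts before 12 months. Section 11.1.1.7 ends duration of response at the first date on which progression is objectively documented.

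**The concern.** Confirmation needs a second assessment about four weeks after the first. The patients least likely to have one are those who deteriorate quickly, because they leave treatment at once, may start another therapy without restriction, and then have no further disease assessments. If progression counts only once confirmed, these patients have no progression on record and the efficacy table censors them when they switch. Kaplan-Meier estimation assumes that a censored patient has the same outlook as those still at risk. Here the patient is censored because the disease has progressed, so the curve is pushed upward.

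The trial has no control arm. Section 2.4.5 hopes for better PFS than in similar patients given pembrolizumab alone, and Section 2.4.3 reports that experience as a 44-week median with 75% progression-free at 6 months. An upward artefact would look like benefit. The documents do not say how the monotherapy trial handled unconfirmed progression, so one cannot assume that the artefact would cancel in the comparison.

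**Working it through.** **Step 1: figures the plan states.** The plan gives no power or precision for PFS. The operating characteristics given for Group 1 efficacy concern ORR: type I error 2% and power 87%, with a stop at 4 or fewer responses in 12 and success at 17 or more in 30. The exact probability of success is the sum over x = 5 to 12 of P(X = x; 12, p) × P(Y ≥ 17 − x; 18, p). This gives 2.15% at p = 0.37 and 86.6% at p = 0.65. The stated figures reproduce, and none depends on PFS.

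**Step 2: one patient under each rule.** The investigator records first progression. The patient is unstable, stops, and starts new therapy before any repeat assessment.

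| Rule applied | PFS outcome |
|---|---|
| Section 11.1.1.3 read literally, efficacy-table censoring | Censored at start of new therapy; a later death is not counted |
| Section 11.1.1.3 read literally, Section 13.1.1.2 censoring | A later death is the event; otherwise censored at last disease assessment |
| Section 13.1.1.2 as written, or Section 11.1.1.5 | Event at first progression; the later therapy is irrelevant |

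The outcomes differ, and no sentence says which rule governs PFS. Nor does either PFS definition (Sections 11.1.1.8 and 13.1.1.2) say whether a confirmed progression is dated to the first or the confirming assessment, a gap of about four weeks.

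**Step 3: illustrative size under the first row.** Inputs:
- median m = 44 weeks, from the monotherapy trial (Section 2.4.3);
- exponential PFS, with all events treated as progressions: an assumption;
- share f of progressions censored at a switch: not in the documents, assumed 10, 20 or 30%.

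The observed hazard is (1 − f) × ln 2 / 44. Hence the apparent median is 44 / (1 − f), and S(26 weeks) = 0.5^[(26/44)(1 − f)].

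| f | Apparent median (weeks) | 6-month PFS |
|---|---|---|
| 0 | 44 | 66% |
| 10% | 44/0.9 = 48.9 | 69% |
| 20% | 44/0.8 = 55.0 | 72% |
| 30% | 44/0.7 = 62.9 | 75% |

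**Step 4: sensitivity to the model.** The exponential gives 66% at 6 months, but the monotherapy trial reported 75%. Starting from 75%, 0.75^(1 − f) gives 77, 79 and 82%. A Kaplan-Meier simulation with 30 patients, 104 weeks of follow-up and switches 0 to 4 weeks after first progression gave typical medians of 46, 50, 55 and 64 weeks for f = 0, 10, 20 and 30%, and the same rounded 6-month values as the table. If only progressions before week 26 are affected, censoring 25, 50 or 75% of them raises simulated 6-month PFS from 66% to 74, 82 or 91%.

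**The case against.** The strongest reply is that the plan never makes confirmation a condition for a PFS event. Section 11.1.1.3 can be read as an instruction for assessment. The endpoint is defined in Section 13.1.1.2, which rests on investigator assessment and censors only patients without documented progression or death. Section 11.1.1.5 ties confirmation to stable subjects, and Section 5.8.1 shows its use in detecting pseudoprogression. In the efficacy table only the ORR and ORR12 rows ask for confirmed findings. On this reading the unstable patient is already an event before switching.

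That reading is reasonable, so biased censoring is not a settled feature of the plan. But Section 11.1.1.3 introduces itself as the place where progression is defined, and its rule covers all progressions. The conflict remains.

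Three stronger inferences are tempting and not supported:
- *The worst outcomes are removed.* Even on the literal reading patients contribute time until the switch, deaths before it count, and EFS records the switch as an event.
- *The bias carries into ORR12.* It does not by this route, because new therapy before 12 months is a failure there.
- *DOR has the same dating gap.* Section 11.1.1.7 already uses the first documented progression. Only the censoring wording in the DOR row needs aligning.

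It is also fair that PFS is secondary, is estimated descriptively and has no planned test.

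**Conclusion.** The point holds as a conflict between stated rules that permits an upward-biased PFS. Two analysts could each follow the document and classify the same patient differently, and the choice would be open after the data are seen. The direction of the error under the literal rule is clear, because it turns progressions into censored observations among patients who are doing badly.

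Its size cannot be derived from the documents. The shift from 44 to about 49, 55 or 63 weeks, and from 66% to 69, 72 or 75% at 6 months, rests on an assumed affected share, an assumed exponential curve and another trial's median. It shows what a modest share could do and is not a forecast. The primary ORR analysis and the futility rule are unaffected. The plan should be clarified before PFS is analysed.

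**What to change.** State in Section 13.1.1.2 and in the PFS row of the efficacy table that:
- the PFS event date is the first documented progression, including when it is later confirmed;
- progression left unconfirmed because of clinical instability, new therapy, death or lack of a further assessment counts as an event on that date;
- only progression refuted by the repeat assessment is disregarded.

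Choose one censoring point for patients with no such event, since Section 13.1.1.2 and the table now differ. For the PFS analysis, reconcile Sections 11.1.1.3, 11.1.1.5 and 13.1.1.2, the table, and the palliative-radiation rule in Section 5.3.1.2. Align the DOR row with Section 11.1.1.7. Add a sensitivity analysis of PFS with start of new significant therapy as an event. Keep the confirmation requirement for response.

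This is analysis wording only. It alters no treatment rule, assessment schedule or sample size. The cost is that reported PFS may look slightly less favourable.
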